**Appendix D: Rules for Determining “Worst” Value**

**“Worst” Clinical Laboratory Value**

Rule	Parameters
Highest value	Hematology: eosinophils, basophils, monocytes, reticulocytes
	Serum chemistry: ALT, AST, ALK-P, creatinine, total bilirubin, urea (nitrogen), uric acid, LDH, creatine kinase, GGT
Lowest value	Hematology: neutrophils, RBC count, HCT, hemoglobin, platelets
	Serum chemistry: albumin, creatinine clearance total protein
Farthest from normal range midpoint	Hematology: WBC count, lymphocytes, MCV, MCH, MCHC
	Serum chemistry: glucose (random), Na, K, phosphate, calcium, chloride

**“Worst” Vital Sign and Weight Measurement**

Parameter	Criterion for “Worst” Vital Sign
Systolic blood pressure	Value farthest from 125 mmHg
Diastolic blood pressure	Value farthest from 75 mmHg
Pulse	Value farthest from 75 beats per minute
Temperature	Highest
Respiratory Rate	Highest
Weight	Greatest weight loss from baseline

**“Worst” ECG Measurement**

Parameter	Criterion for “Worst” ECG
PR	Highest
QT (QTcF and QTcB)	Highest
QRS	Value farthest from midpoint of normal range
Heart Rate	Value farthest from midpoint of normal range

### Appendix E: Rules for Scoring the MMSE

The MMSE score ranges from 0 to 30, and is defined as the sum of 11 items as listed in the following table.

Item	Maximum Score
Orientation – Time (including questions about year, season, month, week, date)	5
Orientation – Place (including questions about state, county, city/town, building and floor)	5
Memory – Registration (including registration word 1-3)	3
Attention and Concentration (including five “what is 100 taken away 7” questions)	5
Memory – Recall (including questions of “Recall Word” 1-3 )	3
Language – Naming (including questions about pencil/pen and watch)	2
Language – Repetition (“Repeat what I say”)	1
Language – Reading Comprehension (“Close your eyes”)	1
Praxis – Ideational (Including questions of “Take in right hand” “Fold in Half” “Put on Floor”).	3
Language – Writing Spontaneous (“Please Write a Sentence”)	1
Praxis – Copying Drawing (“Please copy this design”)	1
Total	30

Some of the item scores are simple sums of sub-item scores. If a sub-item is missing for these items, the maximum score for the item is reduced correspondingly. The following rule will then be used to calculate the MMSE score: Let  $s$  denote the sum of the scores of non-missing items, and  $m$  denote the sum of maximum possible scores of the non-missing items. If  $m/30 \geq 2/3$ , then MMSE score =  $30 \times s/m$ . Otherwise the MMSE score will be missing.

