8 OTHER ASSESSMENTS

8.1 Mini-Mental State Examination (MMSE)

The MMSE (Folstein *et al.*, 1975) was originally developed to differentiate between psychiatric patients with functional and organic conditions, to quantify the level of cognitive impairment, and to monitor changes over time. The MMSE subsequently has become a widely used and extensively validated cognitive test demonstrating satisfactory reliability, validity, and change sensitivity under a wide variety of conditions (Tombaugh and McIntyre, 1992).

Over a 12-month period, Alzheimer's disease patients might typically show a decline in MMSE score of 2-4 points (Schneider, 2001).

The utility of the MMSE as a means of assessing treatment response in Alzheimer's disease has been questioned (Bowie *et al.*, 1999), but its status as a clinical outcome measure has been supported by the UK National Institute for Clinical Excellence guidance (NICE, 2001). Furthermore, the MMSE has demonstrated an ability to detect change in clinical studies with AChEIs (Birks and Harvey, 2004).

In an epidemiological study (Mukaetova-Ladinska *et al.*, 2000), pre-mortem MMSE scores have been correlated with post-mortem Braak stage (based on the spread of tau pathology through the brain). MMSE is also sensitive to decline in bvFTD (Knopman *et al.*, 2008).

The MMSE will be performed at Baseline (if not available from within the prior 42 days) and approximately every 6 months thereafter (or upon early termination) and at the 4-week follow-up visit (if applicable) by raters deemed appropriate and delegated by the principal investigator. For each individual subject, the MMSE questionnaire to be utilized in this study will be the same version utilized for the subject in the respective originating double-blind study (to maintain longitudinal consistency per subject). The MMSE scores will be used to inform the evaluation for possible serotonin toxicity (to be included in the targeted physical and neurological examinations).

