**Listing 16.2.9.7**  
**Mini-Mental State Examination (MMSE)**  
**Safety Population**  
**Part 1 of 3**

Subject ID	Visit	Date Performed (Study Day)	Start Time	End Time	Rater's Initials	Orientation to Time					Orientation to Place	
						What is the year?	What is the season?	What is the month of the year?	What is the day of the week?	What is the date?	What is the state (province)?	What is the country (or city/town?)
xxxxxx	Screening	date9. (xx)	time5.	time5.	XX	0/1	0/1	0/1	0/1	0/1	0/1	0/1
	Week 26	date9. (xx)	time5.	time5.	XX	0/1	0/1	0/1	0/1	0/1	0/1	0/1
xxxxxx	Screening	date9. (xx)	time5.	time5.	XX	0/1	0/1	0/1	0/1	0/1	0/1	0/1
	Week 26	date9. (xx)	time5.	time5.	XX	0/1	0/1	0/1	0/1	0/1	0/1	0/1
xxxxxx	Screening	date9. (xx)	time5.	time5.	XX	0/1	0/1	0/1	0/1	0/1	0/1	0/1
	Week 26	date9. (xx)	time5.	time5.	XX	0/1	0/1	0/1	0/1	0/1	0/1	0/1
xxxxxx	Screening	date9. (xx)	time5.	time5.	XX	0/1	0/1	0/1	0/1	0/1	0/1	0/1
	Week 26	date9. (xx)	time5.	time5.	XX	0/1	0/1	0/1	0/1	0/1	0/1	0/1

 'N/A' is displayed if the version of the MMSE used did not include this question.

 Calculated total score may include imputation of missing items.

Note: Study day is calculated as days since the date of first dose of study drug.

path\l\_program.sas date time

*Programming note: Sort by subject ID. Display the CRF visit label. Include data collected from both the MMSE and MMSE W/O World Backwards CRF pages.*

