**Listing 16.2.9.7**  
**Mini-Mental State Examination (MMSE)**  
**Safety Population**  
**Part 2 of 3**

Subject ID	Visit	Orientation to Place			Registration			Attention and Calculation						
		What is the city/town (or part of city/ neighborhood)?	What is the building (name or type)?	What is the floor of the building (room number or address)?	Word 1	Word 2	Word 3	What is 100 taken away 7?	Keep going #1	Keep going #2	Keep going #3	Keep going #4	Spell WORLD 	
xxxxxx	Screening	0/1	0/1	0/1	0/1	0/1	0/1	0/1	0/1	0/1	0/1	0/1	0/1	0/5
	Week 26	0/1	0/1	0/1	0/1	0/1	0/1	0/1	0/1	0/1	0/1	0/1	0/1	0/5
xxxxxx	Screening	0/1	0/1	0/1	0/1	0/1	0/1	0/1	0/1	0/1	0/1	0/1	0/1	0/5
	Week 26	0/1	0/1	0/1	0/1	0/1	0/1	0/1	0/1	0/1	0/1	0/1	0/1	0/5
xxxxxx	Screening	0/1	0/1	0/1	0/1	0/1	0/1	0/1	0/1	0/1	0/1	0/1	0/1	0/5
	Week 26	0/1	0/1	0/1	0/1	0/1	0/1	0/1	0/1	0/1	0/1	0/1	0/1	0/5
xxxxxx	Screening	0/1	0/1	0/1	0/1	0/1	0/1	0/1	0/1	0/1	0/1	0/1	0/1	0/5
	Week 26	0/1	0/1	0/1	0/1	0/1	0/1	0/1	0/1	0/1	0/1	0/1	0/1	0/5

 'N/A' is displayed if the version of the MMSE used did not include this question.

 Calculated total score may include imputation of missing items.

path\l\_program.sas date time

*Programming note: Sort by subject ID. Display the CRF visit label.*

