**Listing 16.2.9.7**  
**Mini-Mental State Examination (MMSE)**  
**Safety Population**  
**Part 3 of 3**

Subject ID	Visit	Recall			Naming		Comprehension							Calculated		
		Word 1	Word 2	Word 3	1. What is this?	2. What is this?	Repetition	Take in Right Hand	Fold in Half	Put on Floor	Reading	Writing	Drawing	Total Score	Total Score 	
xxxxxx	Screening Week 26	0/1	0/1	0/1	0/1	0/1	0/1	0/1	0/1	0/1	0/1	0/1	0/1	0/1	xx	xx
		0/1	0/1	0/1	0/1	0/1	0/1	0/1	0/1	0/1	0/1	0/1	0/1	0/1	xx	xx
xxxxxx	Screening Week 26	0/1	0/1	0/1	0/1	0/1	0/1	0/1	0/1	0/1	0/1	0/1	0/1	0/1	xx	xx
		0/1	0/1	0/1	0/1	0/1	0/1	0/1	0/1	0/1	0/1	0/1	0/1	0/1	xx	xx
xxxxxx	Screening Week 26	0/1	0/1	0/1	0/1	0/1	0/1	0/1	0/1	0/1	0/1	0/1	0/1	0/1	xx	xx
		0/1	0/1	0/1	0/1	0/1	0/1	0/1	0/1	0/1	0/1	0/1	0/1	0/1	xx	xx
xxxxxx	Screening Week 26	0/1	0/1	0/1	0/1	0/1	0/1	0/1	0/1	0/1	0/1	0/1	0/1	0/1	xx	xx
		0/1	0/1	0/1	0/1	0/1	0/1	0/1	0/1	0/1	0/1	0/1	0/1	0/1	xx	xx

 'N/A' is displayed if the version of the MMSE used did not include this question.

 Calculated total score may include imputation of missing items.

path\l\_program.sas date time

*Programming note: Sort by subject ID. Display the CRF visit label.*

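### SAP Appendix E prorates the MMSE when the serial sevens are blank, even where a Spell WORLD score was recorded for the same five points

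*SAP*

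**What the plan says.** SAP Appendix E states that the MMSE score "is defined as the sum of 11 items as listed in the following table". The five-point attention row of that table reads "Attention and Concentration (including five “what is 100 taken away 7” questions"; no other source for those points is named. On blanks the rule is "If a sub-item is missing for these items, the maximum score for the item is reduced correspondingly". With s the points scored and m the maximum available on what was completed, the total is 30 x s/m if m/30 is at least 2/3. "Otherwise the MMSE score will be missing" covers the rest.

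The layout of Listing 16.2.9.7 (SAP Appendix I) shows that more is collected than Appendix E uses. It has a Spell WORLD column, displayed as 0/5, beside the five serial-sevens columns. A footnote says that N/A "is displayed if the version of the MMSE used did not include this question", and the programming note reads "Include data collected from both the MMSE and MMSE W/O World Backwards CRF pages". The listing carries two totals, Total Score and Calculated Total Score. The footnote "Calculated total score may include imputation of missing items" is attached to the second only.

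Protocol 8.1 keeps each subject on the MMSE version used in the originating study. SAP 8.1 models change in MMSE for subjects with AD in a repeated-measures mixed model, reported in Table 14.2.1.2; Table 14.2.1.1 gives the observed means.

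**The concern.** Proration is a way to fill points for which nothing was observed. On the CRF page that includes WORLD, a result may have been observed for exactly the five points being filled. Appendix E gives no instruction to use it, so a programmer who follows the text will extrapolate from the remaining items and leave the recorded score out.

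The MMSE is the only outcome this SAP models, and Table 14.2.1.2 reports it with 95% confidence intervals. Neither MMSE table layout shows how many totals were prorated. SAP 8.1 specifies no sensitivity analysis, so a reader of the tables could not tell whether the scoring rule mattered.

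**Working it through.** **Inputs.** From SAP Appendix E: the eleven item maxima, the formula 30 x s/m and the 2/3 condition. From Listing 16.2.9.7: WORLD scored 0 to 5. From protocol 8.1: a typical decline of 2-4 points over 12 months in Alzheimer's disease. The value s = 15 is an illustration, not a figure from the documents.

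**1. The plan's own total.** 5 + 5 + 3 + 5 + 3 + 2 + 1 + 1 + 3 + 1 + 1 = 30, as stated. Without Attention the other items sum to 30 - 5 = 25. Adding both sevens and WORLD would give 25 + 5 + 5 = 35, so on a 30-point scale WORLD can only be an alternative source for the same five points.

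**2. The threshold.** m/30 >= 2/3 means m >= 20, so up to 10 points may be blank. At m = 19 the total is missing. With only the sevens blank, m = 25 and proration applies.

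**3. Sevens blank, 15 points on the other 25.** The total is 30 x 15/25 = 18. The five blank points receive 18 - 15 = 3, which is the 60% success rate on the rest (15/25). Had the sevens been entered as 0, m would be 30 and the total 15.

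**4. The same subject with WORLD recorded as w.** The total using WORLD is 15 + w, and the difference is 18 - (15 + w) = 3 - w.

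| WORLD score | Total using WORLD | Appendix E total | Difference |
|---|---|---|---|
| 0 | 15 | 18 | +3 |
| 1 | 16 | 18 | +2 |
| 2 | 17 | 18 | +1 |
| 3 | 18 | 18 | 0 |
| 4 | 19 | 18 | -1 |
| 5 | 20 | 18 | -2 |

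For any s the difference is 30s/25 - (s + w) = s/5 - w. The two agree only when WORLD happens to equal the subject's success rate on the rest.

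**5. Proration in general.** Credit for blank points is 30s/m - s = s(30 - m)/m.

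| s | Credit at m = 25 | Credit at m = 20 |
|---|---|---|
| 5 | 1 | 2.5 |
| 10 | 2 | 5 |
| 15 | 3 | 7.5 |
| 20 | 4 | 10 |

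The largest possible credit is 10, when 20 of 20 becomes 30. For a fixed number of blanks the credit falls as s falls.

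**6. Scale.** A difference of +3 in one subject lies inside the 2-4 point yearly decline that protocol 8.1 calls typical. The documents do not say how many totals are affected, so no effect on a mean can be derived.

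**The case against.** Appendix E is silent on WORLD rather than excluding it, and its attention row introduces the sevens with the word including. That is fair, but the total is defined by the listed items and WORLD is not among them. A rule that two programmers could implement differently needs settling before the tables are run.

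Scoring only the sevens also derives every total in the same way on both CRF pages. Bringing in WORLD makes the source of Attention depend on the page, because WORLD can stand in only where it was collected. This objection stands as a cost. Keeping the version constant within subject limits it but does not remove it, since one subject could have sevens at one visit and WORLD at another.

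The protocol has no efficacy endpoints and plans no inferential statistics. The listing discloses imputation and shows item-level data with both totals. This limits the importance of the point. It does not help a reader of Tables 14.2.1.1 and 14.2.1.2, where nothing marks a prorated value.

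One might go further and allow proration only at, say, 27 of 30 points. That would make every total with the whole Attention item blank (m = 25) missing, and could itself remove deteriorating subjects. The documents give no basis for that cut-off.

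**Conclusion.** The point holds in a limited form. As written, Appendix E replaces an observed WORLD result by an extrapolated one whenever all five sevens are blank and WORLD was scored. At s = 15 on the other 25 points the error is between +3 and -2 points in the individual total. This assumes that such records exist, which the documents do not show, and that WORLD is an acceptable measure of the Attention item.

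A reader might infer three stronger things that the documents do not support.

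- **That items a subject could not do are credited as answered.** Nothing says that inability or refusal is coded as missing. The listing shows sub-items as 0/1, and a failure entered as 0 stays in the denominator and earns nothing. A blank earns pro-rata credit, 3 of 5 in the example, not full credit.
- **That decline is biased towards looking slower.** That depends on how sites code unable or refused items and how often items are blank at each visit, neither of which is given. Credit shrinks as s falls for the same number of blanks, and against a WORLD score of 4 or 5 proration understates the total in the example.
- **That safety monitoring is weakened.** Protocol 8.1 does say "The MMSE scores will be used to inform the evaluation for possible serotonin toxicity", but proration is an analysis derivation. Nothing shows investigators using the calculated score.

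**What to change.** Make three changes to the SAP.

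1. In Appendix E, add that when all five serial-sevens sub-items are blank and WORLD was recorded, the WORLD score is the Attention item score and those five points count in m.
2. Report the number of prorated totals by visit alongside the MMSE tables.
3. Repeat Tables 14.2.1.1 and 14.2.1.2 with the recorded Total Score already in Listing 16.2.9.7, as a sensitivity analysis. State how that total treats blanks and WORLD, because the listing layout does not say.

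The cost is a few lines of SAP wording, one count and one repeat of two tables, with no new data collection. The downside is that WORLD and serial sevens may differ in difficulty, so a subject whose Attention source changes between visits could show a change that comes from the instrument. Apart from the added WORLD rule, the proration formula and its 2/3 condition can stay as they are.

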## Appendix F: List of Tables, Figures and Listings

### List of Tables

Table Number	Table Description
14.1.1.1	Subject Disposition (All Subjects)
14.1.1.2	Subject Disposition by Region (All Subjects)
14.1.1.3	Subject Disposition by Country and Site (All Subjects)
14.1.1.4	Subject Disposition – Non-AChEI/Memantine Users (All Subjects)
14.1.2.1	Study Discontinuation by Time Period (Safety Population)
14.1.2.2	Study Discontinuation by Time Period – Non-AChEI/Memantine Users (Safety Population)
14.1.2.3	Study Discontinuation by Time Period and by Region (Safety Population)
14.1.3.1	Protocol Deviations (Safety Population)
14.1.3.2	Protocol Deviations by Critical, Major and Minor Categories (Safety Population)
14.1.4.1	Demographic and Baseline Characteristics (Safety Population)
14.1.4.2	Demographic and Baseline Characteristics – Non-AChEI/Memantine Users (Safety Population)
14.1.5.1	Medical History (Safety Population)
14.1.5.2	Medical History – Non-AChEI/Memantine Users (Safety Population)
14.1.6.1.1	Concomitant Medications Ongoing On Day 1 of Dosing (Pre-existing Medications) (Safety Population)
14.1.6.1.2	Concomitant Medications Ongoing On Day 1 of Dosing (Pre-existing Medications) – Non-AChEI/Memantine Users (Safety Population)
14.1.6.2.1	Concomitant Medications that Started On or After Day 1 of Dosing (Study-emergent Medications) (Safety Population)
14.1.6.2.2	Concomitant Medications that Started On or After Day 1 of Dosing (Study-emergent Medications) – Non-AChEI/Memantine Users (Safety Population)
14.1.6.3.1	Concomitant Medications (Pre-existing and Study-emergent Medications) (Safety Population)
14.1.6.3.2	Concomitant Medications (Pre-existing and Study-emergent Medications) – Non-AChEI/Memantine Users (Safety Population)
14.2.1.1	MMSE (Safety Population: Subjects with AD)

Table Number	Table Description
14.2.1.2	MMSE Annualized LS Means (Safety Population: Subjects with AD)
14.2.2	RUD Lite (Safety Population: Subjects with at Least One Post-Baseline RUD Lite Questionnaire)
14.2.3	EQ-5D-5L (Safety Population: Subjects with at Least One Post-Baseline EQ-5D-5L Questionnaire)
14.3.1.1	Study Drug Exposure and Compliance (Safety Population)
14.3.1.2	Study Drug Exposure and Compliance – Non-AChEI/Memantine Users (Safety Population)
14.3.2.1.1.1	Overall Summary of Adverse Events Ongoing On Day 1 of Dosing (Pre-existing Adverse Events) (Safety Population)
14.3.2.1.1.2	Overall Summary of Adverse Events Ongoing On Day 1 of Dosing (Pre-existing Adverse Events) – Non-AChEI/Memantine Users (Safety Population)
14.3.2.1.2.1	Overall Summary of Adverse Events that Started On or After Day 1 of Dosing (Study-emergent Adverse Events) (Safety Population)
14.3.2.1.2.2	Overall Summary of Adverse Events that Started On or After Day 1 of Dosing (Study-emergent Adverse Events) – Non-AChEI/Memantine Users (Safety Population)
14.3.2.1.3.1	Overall Summary of Adverse Events (Pre-existing Adverse Events and Study-emergent Adverse Events) (Safety Population)
14.3.2.1.3.2	Overall Summary of Adverse Events (Pre-existing Adverse Events and Study-emergent Adverse Events) – Non-AChEI/Memantine Users (Safety Population)
14.3.2.1.3.3	Overall Summary of Adverse Events (Pre-existing Adverse Events and Study-emergent Adverse Events) by Diagnosis and Prior Study Treatment (Safety Population)
14.3.2.2.1.1	Adverse Events Ongoing On Day 1 of Dosing (Pre-existing Adverse Events) by System Organ Class and Preferred Term (Safety Population)
14.3.2.2.1.2	Adverse Events Ongoing On Day 1 of Dosing (Pre-existing Adverse Events) by System Organ Class and Preferred Term – Non-AChEI/Memantine Users (Safety Population)
14.3.2.2.2.1	Adverse Events that Started On or After Day 1 of Dosing (Study-emergent Adverse Events) by System Organ Class and Preferred Term (Safety Population)

Table Number	Table Description
14.3.2.2.2.2	Adverse Events that Started On or After Day 1 of Dosing (Study-emergent Adverse Events) by System Organ Class and Preferred Term – Non-AChEI/Memantine Users (Safety Population)
14.3.2.2.3.1	Adverse Events (Pre-existing Adverse Events and Study-emergent Adverse Events) by System Organ Class and Preferred Term (Safety Population)
14.3.2.2.3.2	Adverse Events (Pre-existing Adverse Events and Study-emergent Adverse Events) by System Organ Class and Preferred Term – Non-AChEI/Memantine Users (Safety Population)
14.3.2.2.3.3	Adverse Events (Pre-existing Adverse Events and Study-emergent Adverse Events) by Diagnosis, Prior Study Treatment, System Organ Class and Preferred Term (Safety Population)
14.3.2.3.1.1	Adverse Events Ongoing On Day 1 of Dosing (Pre-existing Adverse Events) by System Organ Class, Preferred Term and Severity (Safety Population)
14.3.2.3.1.2	Adverse Events Ongoing On Day 1 of Dosing (Pre-existing Adverse Events) by System Organ Class, Preferred Term and Severity – Non-AChEI/Memantine Users (Safety Population)
14.3.2.3.2.1	Adverse Events that Started On or After Day 1 of Dosing (Study-emergent Adverse Events) by System Organ Class, Preferred Term and Severity (Safety Population)
14.3.2.3.2.2	Adverse Events that Started On or After Day 1 of Dosing (Study-emergent Adverse Events) by System Organ Class, Preferred Term and Severity – Non-AChEI/Memantine Users (Safety Population)
14.3.2.3.3.1	Adverse Events (Pre-existing Adverse Events and Study-emergent Adverse Events) by System Organ Class, Preferred Term and Severity (Safety Population)
14.3.2.3.3.2	Adverse Events (Pre-existing Adverse Events and Study-emergent Adverse Events) by System Organ Class, Preferred Term and Severity – Non-AChEI/Memantine Users (Safety Population)
14.3.2.4.1.1	Adverse Events Ongoing On Day 1 of Dosing (Pre-existing Adverse Events) by System Organ Class, Preferred Term and Relationship (Safety Population)
14.3.2.4.1.2	Adverse Events Ongoing On Day 1 of Dosing (Pre-existing Adverse Events) by System Organ Class, Preferred Term and Relationship – Non-AChEI/Memantine Users (Safety Population)

Table Number	Table Description
14.3.2.4.2.1	Adverse Events that Started On or After Day 1 of Dosing (Study-emergent Adverse Events) by System Organ Class, Preferred Term and Relationship (Safety Population)
14.3.2.4.2.2	Adverse Events that Started On or After Day 1 of Dosing (Study-emergent Adverse Events) by System Organ Class, Preferred Term and Relationship – Non-AChEI/Memantine Users (Safety Population)
14.3.2.4.3.1	Adverse Events (Pre-existing Adverse Events and Study-emergent Adverse Events) by System Organ Class, Preferred Term and Relationship (Safety Population)
14.3.2.4.3.2	Adverse Events (Pre-existing Adverse Events and Study-emergent Adverse Events) by System Organ Class, Preferred Term and Relationship – Non-AChEI/Memantine Users (Safety Population)
14.3.2.5.1.1	Serious Adverse Events Ongoing On Day 1 of Dosing (Pre-existing Adverse Events) by System Organ Class and Preferred Term (Safety Population)
14.3.2.5.1.2	Serious Adverse Events Ongoing On Day 1 of Dosing (Pre-existing Adverse Events) by System Organ Class and Preferred Term – Non-AChEI/Memantine Users (Safety Population)
14.3.2.5.2.1	Serious Adverse Events that Started On or After Day 1 of Dosing (Study-emergent Adverse Events) by System Organ Class and Preferred Term (Safety Population)
14.3.2.5.2.2	Serious Adverse Events that Started On or After Day 1 of Dosing (Study-emergent Adverse Events) by System Organ Class and Preferred Term – Non-AChEI/Memantine Users (Safety Population)
14.3.2.5.3.1	Serious Adverse Events (Pre-existing Adverse Events and Study-emergent Adverse Events) by System Organ Class and Preferred Term (Safety Population)
14.3.2.5.3.2	Serious Adverse Events (Pre-existing Adverse Events and Study-emergent Adverse Events) by System Organ Class and Preferred Term – Non-AChEI/Memantine Users (Safety Population)
14.3.2.6.1.1	Fatal Adverse Events Ongoing On Day 1 of Dosing (Pre-existing Adverse Events) by System Organ Class and Preferred Term (Safety Population)
14.3.2.6.1.2	Fatal Adverse Events Ongoing On Day 1 of Dosing (Pre-existing Adverse Events) by System Organ Class and Preferred Term – Non-AChEI/Memantine Users (Safety Population)

Table Number	Table Description
14.3.2.6.2.1	Fatal Adverse Events that Started On or After Day 1 of Dosing (Study-emergent Adverse Events) by System Organ Class and Preferred Term (Safety Population)
14.3.2.6.2.2	Fatal Adverse Events that Started On or After Day 1 of Dosing (Study-emergent Adverse Events) by System Organ Class and Preferred Term – Non-AChEI/Memantine Users (Safety Population)
14.3.2.6.3.1	Fatal Adverse Events (Pre-existing Adverse Events and Study-emergent Adverse Events) by System Organ Class and Preferred Term (Safety Population)
14.3.2.6.3.2	Fatal Adverse Events (Pre-existing Adverse Events and Study-emergent Adverse Events) by System Organ Class and Preferred Term – Non-AChEI/Memantine Users (Safety Population)
14.3.2.7.1.1	Non-Fatal Serious Adverse Events Ongoing On Day 1 of Dosing (Pre-existing Adverse Events) by System Organ Class and Preferred Term (Safety Population)
14.3.2.7.1.2	Non-Fatal Serious Adverse Events Ongoing On Day 1 of Dosing (Pre-existing Adverse Events) by System Organ Class and Preferred Term – Non-AChEI/Memantine Users (Safety Population)
14.3.2.7.2.1	Non-Fatal Serious Adverse Events that Started On or After Day 1 of Dosing (Study-emergent Adverse Events) by System Organ Class and Preferred Term (Safety Population)
14.3.2.7.2.2	Non-Fatal Serious Adverse Events that Started On or After Day 1 of Dosing (Study-emergent Adverse Events) by System Organ Class and Preferred Term – Non-AChEI/Memantine Users (Safety Population)
14.3.2.7.3.1	Non-Fatal Serious Adverse Events (Pre-existing Adverse Events and Study-emergent Adverse Events) by System Organ Class and Preferred Term (Safety Population)
14.3.2.7.3.2	Non-Fatal Serious Adverse Events (Pre-existing Adverse Events and Study-emergent Adverse Events) by System Organ Class and Preferred Term – Non-AChEI/Memantine Users (Safety Population)
14.3.2.8.1.1	Serious Adverse Reactions Ongoing On Day 1 of Dosing (Pre-existing Adverse Events) by System Organ Class and Preferred Term (Safety Population)
14.3.2.8.1.2	Serious Adverse Reactions Ongoing On Day 1 of Dosing (Pre-existing Adverse Events) by System Organ Class and Preferred Term – Non-AChEI/Memantine Users (Safety Population)

Table Number	Table Description
14.3.2.8.2.1	Serious Adverse Reactions that Started On or After Day 1 of Dosing (Study-emergent Adverse Events) by System Organ Class and Preferred Term (Safety Population)
14.3.2.8.2.2	Serious Adverse Reactions that Started On or After Day 1 of Dosing (Study-emergent Adverse Events) by System Organ Class and Preferred Term – Non-AChEI/Memantine Users (Safety Population)
14.3.2.8.3.1	Serious Adverse Reactions (Pre-existing Adverse Events and Study-emergent Adverse Events) by System Organ Class and Preferred Term (Safety Population)
14.3.2.8.3.2	Serious Adverse Reactions (Pre-existing Adverse Events and Study-emergent Adverse Events) by System Organ Class and Preferred Term – Non-AChEI/Memantine Users (Safety Population)
14.3.2.9.1.1	Severe Adverse Events Ongoing On Day 1 of Dosing (Pre-existing Adverse Events) by System Organ Class and Preferred Term (Safety Population)
14.3.2.9.1.2	Severe Adverse Events Ongoing On Day 1 of Dosing (Pre-existing Adverse Events) by System Organ Class and Preferred Term – Non-AChEI/Memantine Users (Safety Population)
14.3.2.9.2.1	Severe Adverse Events that Started On or After Day 1 of Dosing (Study-emergent Adverse Events) by System Organ Class and Preferred Term (Safety Population)
14.3.2.9.2.2	Severe Adverse Events that Started On or After Day 1 of Dosing (Study-emergent Adverse Events) by System Organ Class and Preferred Term – Non-AChEI/Memantine Users (Safety Population)
14.3.2.9.3.1	Severe Adverse Events (Pre-existing Adverse Events and Study-emergent Adverse Events) by System Organ Class and Preferred Term (Safety Population)
14.3.2.9.3.2	Severe Adverse Events (Pre-existing Adverse Events and Study-emergent Adverse Events) by System Organ Class and Preferred Term – Non-AChEI/Memantine Users (Safety Population)
14.3.2.10.1.1	Adverse Events Leading to Dose Reduction that were Ongoing On Day 1 of Dosing (Pre-existing Adverse Events) by System Organ Class and Preferred Term (Safety Population)
14.3.2.10.1.2	Adverse Events Leading to Dose Reduction that were Ongoing On Day 1 of Dosing (Pre-existing Adverse Events) by System Organ Class and Preferred Term – Non-AChEI/Memantine Users (Safety Population)

Table Number	Table Description
14.3.2.10.2.1	Adverse Events Leading to Dose Reduction that Started On or After Day 1 of Dosing (Study-emergent Adverse Events) by System Organ Class and Preferred Term (Safety Population)
14.3.2.10.2.2	Adverse Events Leading to Dose Reduction that Started On or After Day 1 of Dosing (Study-emergent Adverse Events) by System Organ Class and Preferred Term – Non-AChEI/Memantine Users (Safety Population)
14.3.2.10.3.1	Adverse Events Leading to Dose Reduction (Pre-existing Adverse Events and Study-emergent Adverse Events) by System Organ Class and Preferred Term (Safety Population)
14.3.2.10.3.2	Adverse Events Leading to Dose Reduction (Pre-existing Adverse Events and Study-emergent Adverse Events) by System Organ Class and Preferred Term – Non-AChEI/Memantine Users (Safety Population)
14.3.2.10.3.3	Adverse Events Leading to Dose Reduction (Pre-existing Adverse Events and Study-emergent Adverse Events) by Diagnosis, Prior Study Treatment, System Organ Class and Preferred Term (Safety Population)
14.3.2.11.1.1	Adverse Events Leading to Dose Interruption that were Ongoing On Day 1 of Dosing (Pre-existing Adverse Events) by System Organ Class and Preferred Term (Safety Population)
14.3.2.11.1.2	Adverse Events Leading to Dose Interruption that were Ongoing On Day 1 of Dosing (Pre-existing Adverse Events) by System Organ Class and Preferred Term – Non-AChEI/Memantine Users (Safety Population)
14.3.2.11.2.1	Adverse Events Leading to Dose Interruption that Started On or After Day 1 of Dosing (Study-emergent Adverse Events) by System Organ Class and Preferred Term (Safety Population)
14.3.2.11.2.2	Adverse Events Leading to Dose Interruption that Started On or After Day 1 of Dosing (Study-emergent Adverse Events) by System Organ Class and Preferred Term – Non-AChEI/Memantine Users (Safety Population)
14.3.2.11.3.1	Adverse Events Leading to Dose Interruption (Pre-existing Adverse Events and Study-emergent Adverse Events) by System Organ Class and Preferred Term (Safety Population)

Table Number	Table Description
14.3.2.11.3.2	Adverse Events Leading to Dose Interruption (Pre-existing Adverse Events and Study-emergent Adverse Events) by System Organ Class and Preferred Term – Non-AChEI/Memantine Users (Safety Population)
14.3.2.11.3.3	Adverse Events Leading to Dose Interruption (Pre-existing Adverse Events and Study-emergent Adverse Events) by Diagnosis, Prior Study Treatment, System Organ Class and Preferred Term (Safety Population)
14.3.2.12.1.1	Adverse Events Leading to Study Drug Withdrawal that were Ongoing On Day 1 of Dosing (Pre-existing Adverse Events) by System Organ Class and Preferred Term (Safety Population)
14.3.2.12.1.2	Adverse Events Leading to Study Drug Withdrawal that were Ongoing On Day 1 of Dosing (Pre-existing Adverse Events) by System Organ Class and Preferred Term – Non-AChEI/Memantine Users (Safety Population)
14.3.2.12.2.1	Adverse Events Leading to Study Drug Withdrawal that Started On or After Day 1 of Dosing (Study-emergent Adverse Events) by System Organ Class and Preferred Term (Safety Population)
14.3.2.12.2.2	Adverse Events Leading to Study Drug Withdrawal that Started On or After Day 1 of Dosing (Study-emergent Adverse Events) by System Organ Class and Preferred Term – Non-AChEI/Memantine Users (Safety Population)
14.3.2.12.3.1	Adverse Events Leading to Study Drug Withdrawal (Pre-existing Adverse Events and Study-emergent Adverse Events) by System Organ Class and Preferred Term (Safety Population)
14.3.2.12.3.2	Adverse Events Leading to Study Drug Withdrawal (Pre-existing Adverse Events and Study-emergent Adverse Events) by System Organ Class and Preferred Term – Non-AChEI/Memantine Users (Safety Population)
14.3.2.12.3.3	Adverse Events Leading to Study Drug Withdrawal (Pre-existing Adverse Events and Study-emergent Adverse Events) by Diagnosis, Prior Study Treatment, System Organ Class and Preferred Term (Safety Population)
14.3.2.13.1.1	Adverse Events Leading to Dose Reduction, Dose Interruption or Study Drug Withdrawal that were Ongoing On Day 1 of Dosing (Pre-existing Adverse Events) by System Organ Class and Preferred Term (Safety Population)

Table Number	Table Description
14.3.2.13.1.2	Adverse Events Leading to Dose Reduction, Dose Interruption or Study Drug Withdrawal that were Ongoing On Day 1 of Dosing (Pre-existing Adverse Events) by System Organ Class and Preferred Term – Non-AChEI/Memantine Users (Safety Population)
14.3.2.13.2.1	Adverse Events Leading to Dose Reduction, Dose Interruption or Study Drug Withdrawal that Started On or After Day 1 of Dosing (Study-emergent Adverse Events) by System Organ Class and Preferred Term (Safety Population)
14.3.2.13.2.2	Adverse Events Leading to Dose Reduction, Dose Interruption or Study Drug Withdrawal that Started On or After Day 1 of Dosing (Study-emergent Adverse Events) by System Organ Class and Preferred Term – Non-AChEI/Memantine Users (Safety Population)
14.3.2.13.3.1	Adverse Events Leading to Dose Reduction, Dose Interruption or Study Drug Withdrawal (Pre-existing Adverse Events and Study-emergent Adverse Events) by System Organ Class and Preferred Term (Safety Population)
14.3.2.13.3.2	Adverse Events Leading to Dose Reduction, Dose Interruption or Study Drug Withdrawal (Pre-existing Adverse Events and Study-emergent Adverse Events) by System Organ Class and Preferred Term – Non-AChEI/Memantine Users (Safety Population)
14.3.2.13.3.3	Adverse Events Leading to Dose Reduction, Dose Interruption or Study Drug Withdrawal (Pre-existing Adverse Events and Study-emergent Adverse Events) by Diagnosis, Prior Study Treatment, System Organ Class and Preferred Term (Safety Population)
14.3.2.14.1.1	Adverse Events of Special Interest (AESI) Ongoing On Day 1 of Dosing (Pre-existing Adverse Events) by System Organ Class and Preferred Term (Safety Population)
14.3.2.14.1.2	Adverse Events of Special Interest (AESI) Ongoing On Day 1 of Dosing (Pre-existing Adverse Events) by System Organ Class and Preferred Term – Non-AChEI/Memantine Users (Safety Population)
14.3.2.14.2.1	Adverse Events of Special Interest (AESI) that Started On or After Day 1 of Dosing (Study-emergent Adverse Events) by System Organ Class and Preferred Term (Safety Population)
14.3.2.14.2.2	Adverse Events of Special Interest (AESI) that Started On or After Day 1 of Dosing (Study-emergent Adverse Events) by System Organ Class and Preferred Term – Non-AChEI/Memantine Users (Safety Population)

Table Number	Table Description
14.3.2.14.3.1	Adverse Events of Special Interest (AESI) (Pre-existing Adverse Events and Study-emergent Adverse Events) by System Organ Class and Preferred Term (Safety Population)
14.3.2.14.3.2	Adverse Events of Special Interest (AESI) (Pre-existing Adverse Events and Study-emergent Adverse Events) by System Organ Class and Preferred Term – Non-AChEI/Memantine Users (Safety Population)
14.3.2.15.1	Post-Treatment Adverse Events by System Organ Class and Preferred Term (Safety Population)
14.3.2.15.2	Post-Treatment Adverse Events by System Organ Class and Preferred Term – Non-AChEI/Memantine Users (Safety Population)
14.3.3.1.1.1	Hematology Values and Changes from Baseline at All Visits – Conventional Units (Safety Population)
14.3.3.1.1.2	Hematology Values and Changes from Baseline at All Visits – Conventional Units – Non-AChEI/Memantine Users (Safety Population)
14.3.3.1.2.1	Hematology Values and Changes from Baseline at All Visits – SI Units (Safety Population)
14.3.3.1.2.2	Hematology Values and Changes from Baseline at All Visits – SI Units – Non-AChEI/Memantine Users (Safety Population)
14.3.3.2.1.1	Serum Chemistry Values and Changes from Baseline at All Visits – Conventional Units (Safety Population)
14.3.3.2.1.2	Serum Chemistry Values and Changes from Baseline at All Visits – Conventional Units – Non-AChEI/Memantine Users (Safety Population)
14.3.3.2.2.1	Serum Chemistry Values and Changes from Baseline at All Visits – SI Units (Safety Population)
14.3.3.2.2.2	Serum Chemistry Values and Changes from Baseline at All Visits – SI Units – Non-AChEI/Memantine Users (Safety Population)
14.3.3.3.1	Incidence of Potentially Clinically Significant Hematology and Serum Biochemistry Results (Safety Population)
14.3.3.3.2	Incidence of Potentially Clinically Significant Hematology and Serum Biochemistry Results – Non-AChEI/Memantine Users (Safety Population)
14.3.4.1.1.1	Vital Signs (Safety Population)
14.3.4.1.1.2	Vital Signs – Non-AChEI/Memantine Users (Safety Population)
14.3.4.1.2.1	Weight Directional Changes (Safety Population)

Table Number	Table Description
14.3.4.1.2.2	Weight Directional Changes – Non-AChEI/Memantine Users (Safety Population)
14.3.4.1.3.1	Incidence of Potentially Clinically Significant Vital Sign Results (Safety Population)
14.3.4.1.3.2	Incidence of Potentially Clinically Significant Vital Sign Results – Non-AChEI/Memantine Users (Safety Population)
14.3.4.2	Physical Examination by Visit (Safety Population)
14.3.4.3	Neurological Examination by Visit (Safety Population)
14.3.4.4.1	Serotonin Toxicity (Syndrome) Ratings by Visit (Safety Population)
14.3.4.4.2	Serotonin Toxicity (Syndrome) Ratings by Visit – Non-AChEI/Memantine Users (Safety Population)
14.3.4.5.1	Central ECG Data by Visit (Safety Population)
14.3.4.5.2	Central ECG Data – Change from Baseline in Investigator’s Overall Interpretation of Clinical Significance by Visit (Safety Population)
14.3.4.5.3	Central ECG Data – QTc Abnormalities (Safety Population)

